2.2 Other Agents: Not applicable (N/A)

2.3 Study Disease: Malignant Gliomas

Malignant gliomas are the most common type of brain tumor in adults. It is estimated that each year there are approximately 12,000 new cases in the United States. Despite optimal treatment with surgery, radiotherapy and chemotherapy with temozolomide, the prognosis remains poor and almost all patients

Amended:

Reviewed by OCR, JR 3/24/14

develop recurrent or progressive tumor. Patients with glioblastoma (GBM) have a median survival of approximately 14.6 months,(Stupp, Mason et al. 2005) while those with anaplastic astrocytomas (AA) have a median survival of 24 to 36 months. The median survival for patients with recurrent GBM is 6 months and for AA is 11 months. Once patients develop tumor progression, conventional chemotherapy is generally ineffective.

Approximately 70% of GBMs exhibit abnormally activated phosphotidylinositol 3-kinase (PI3K)/AKT signaling, usually as a result of loss or alteration of the tumor suppressor gene phosphatase and tensin homolog on chromosome ten (*PTEN*).(reviewed in [name] and Holland 2006) The PI3K/AKT pathway activates the mammalian target of rapamycin (mTOR) which activates p70S6 Kinase (S6K) and stimulates multiple oncogenic processes including translation of a number of key proteins required for cell-cycle progression. The presence of *PTEN* gene alterations and the subsequent activation of these downstream pathways have been associated with poor prognosis in AA, anaplastic oligodendrogloma (AO) and GBM. Targeting of the components of the PI3K/AKT/mTOR/S6K pathways can result in cell-cycle arrest, apoptosis, or reduced tumorigenicity.

Modeling brain tumors using the RCAS/tv-a system

One of the main objectives highlighted by the *Brain Tumor Progress Review Group (PRG)* was the need for animal models of brain tumors that accurately represent the histology and genetics of the disease in humans. The RCAS/tv-a system produces gliomas that fulfill this objective by achieving cell type-specific gene transfer to somatic cells post-natally. This system was developed by [name], now head of the Brain Tumor Center at Memorial Sloan Kettering Cancer Center. Through glial-specific gene transfer *in vivo*, this system permits determination of the role of single and multiple mutations on gliomagenesis in mice. Modeling with this system demonstrated that the combined activation of RAS/MAPK and PI3K/AKT signaling in GBMs is causal and not an epiphenomenon. Murine gliomas modeled with this system reproduce their human counterparts both histologically and radiographically with high fidelity ([Figure 1](#)).([name] and Holland 2006)

[figure not shown]

Figure 1: RCAS/tv-a modeled high grade gliomas (A,B,C) using forced PDGF overexpression accurately reflect their human counterparts (D,E,F) both histologically (A vs. D) and radiographically on contrast enhanced T1 (B vs. E) and T2 (C vs. F) weighed brain MRI.

2.4 Rationale for combined temsirolimus and perifosine in malignant gliomas

Temsirolimus

Temsirolimus crosses the blood-brain barrier and achieves therapeutic concentrations in brain tumor tissue.(Kuhn, Chang et al. 2007) It is also reasonably well-tolerated with toxicities usually mild including myelosuppression (especially thrombocytopenia), hyperlipidemia, stomatitis, skin rash and fatigue. However, temsirolimus has only modest antitumor activity as a single agent in recurrent high-grade gliomas. For example, the 6 month progression-free survival (6mPFS) rate for patients with recurrent GBM was approximately 2% in a North American Brain Tumor Consortium phase II trial, (Chang et al. 2005) and approximately 8% in a North Central Cancer Treatment Group phase II trial (Galanis et al. 2005). Possible explanations for the limited efficacy include the existence of mTOR independent activities of AKT uninhibited by temsirolimus, and the observation in other cell types that mTOR inhibition leads to upstream activation of AKT itself through a feedback loop.(Sun et al. 2005;

Amended:

Reviewed by OCR, JR 3/24/14

O'Reilly *et al.* 2006)

Perifosine

There has been extensive pre-clinical testing of perifosine in glia *in vitro* and in modeled gliomas *in vivo* in [name] laboratory at Memorial Sloan Kettering Cancer Center (MSKCC). For example, perifosine specifically has been shown to inhibit AKT signaling in transformed glia (Momota *et al.* 2005) as well as reduce proliferation of modeled gliomas in mice.(Momota *et al.* 2005; also reviewed in Lyustikman and [name] 2006)

Based on these preclinical data, as well as the promising results of numerous phase I and II trials in patients with sarcomas and other solid tumors, in 2006 we conceived, wrote, and opened an investigator ([name]) initiated phase II trial of perifosine monotherapy at MSKCC for patients with recurrent malignant gliomas. This was the first step in the translation of our extensive preclinical glioma data with perifosine into human glioma trials. Toxicity was minimal among 25 patients enrolled to date, with 1 episode each of grade 1 diarrhea, grade 1 nausea, grade 4 joint pain, and grade 3 difficulty walking as the only significant adverse events possibly, probably, or definitely related to perifosine. The known toxicities of perifosine include nausea, diarrhea, and exacerbation of gout; the joint pain was likely a gouty attack in a patient without a prior known gout diagnosis. Preliminary efficacy results, reported at the 2007 Society for Neuro-Oncology annual meeting, included 2 partial radiographic responses among 6 evaluable patients with recurrent anaplastic gliomas.. However, none of the first 12 patients with GBM reached 6 months of progression-free survival which was the primary efficacy endpoint; therefore, in accordance with the statistical design of the trial, accrual of patients with GBM was terminated because it was statistically unlikely (90% power) that the 6mPFS rate would reach or exceed 20%, the threshold to consider monotherapy with perifosine as promising for recurrent GBM.

Although temsirolimus and perifosine have only limited activity as single agents, we explored the possibility that combinations of these agents could have synergistic therapeutic efficacy. While the phase II trial of perifosine monotherapy for recurrent gliomas has been ongoing, further pre-clinical evaluation of perifosine in combination with temsirolimus has been conducted. In modeled gliomas, perifosine reduces pAKT and reduces proliferation, but there is only minimal killing of tumor cells and only regional cell cycle arrest. In addition, despite the reduction in pAKT, the activity of the mTOR effector S6RP (assayed by pS6RP) is not decreased *in vivo* and may actually rise during perifosine treatment for reasons that remain unclear at this time. By contrast, temsirolimus reduces pS6RP levels and arrests proliferation, but also only causes minimal cell death. However, when the two agents are administered together, the combination induces widespread cell death, arrest of surviving cells, and inhibition of the entire AKT signal transduction cascade including both pAKT and pS6RP. Therefore, this extensive preclinical data suggests combining perifosine and temsirolimus has both superior anti-

Amended:

Reviewed by OCR, JR 3/24/14

Memorial Sloan Kettering Cancer Center
IRB Protocol

IRB#: 09-058 A(14)

tumor effects and superior inhibition of the AKT signal transduction cascade than either agent alone. For example, three-day treatment of perifosine (30mg/kg) in combination with temsirolimus (40mg/kg) leads to massive necrosis and cell cycle arrest almost in all treated mice (n=13). From the perspective of a clinical trial, with the exception of nausea/vomiting and diarrhea, the two agents have non-overlapping toxicities when used alone, and may therefore allow therapeutic doses of each drug together without substantial side effects.

The maximum tolerated dose (MTD) of combined temsirolimus and perifosine is required for a phase II study. Therefore, we will conduct a phase I/II study to both determine the MTD, safety, and efficacy of the combined drug therapy. We will also analyze pre-treatment archival tissue to identify molecular predictors of response and also assess tissue resected during therapy (through a surgical substudy as part of the phase II component) to determine molecular effects of the combination in human malignant gliomas *in vivo*.

Study Design and Rationale

Phase I Component

The phase I component of the study will define the maximum tolerated dose (MTD) of temsirolimus in combination with perifosine in patients with recurrent malignant gliomas not on EIAED.

Temsirolimus is metabolized by cytochrome P450 3A4 which is induced by EIAED. As a result the therapeutic doses of temsirolimus, and to a lesser extent, perifosine, will be higher for patients on EIAED than for patients not taking these medications. Therefore, to reduce the study complexity and the number of patients required, eligibility will be restricted to patients not taking EIAED. If the combination of temsirolimus and perifosine shows efficacy, a separate phase I study to determine the MTD in patients on EIAED will be considered. Standard dose escalation in groups of three will be performed.

All patients will initially receive both drugs and none will receive placebo. There is no intra-patient dose escalation. The starting dose of perifosine will consist of a loading dose of 600 mg on day 1 followed by a fixed maintenance dose of 100 mg per day for days 2-28 of each 28 day cycle. Patients will receive an initial dose of temsirolimus of 15 mg intravenously once weekly. Depending on patient tolerance, subsequent temsirolimus doses will be escalated to a maximum of 170 mg intravenously weekly in subsequent cohorts with one final cohort comprised of an escalated perifosine dose. The maximum tolerated dose of temsirolimus will be based on the assessment of dose limiting toxicity DLT during the first 28 days of treatment only (cycle 1). If excessive toxicity is encountered with the combination of temsirolimus and perifosine, the doses will be reduced per [section 6](#).

Phase II Component

The primary goal of the phase II component of the study is to determine the therapeutic efficacy of the combination of temsirolimus and perifosine in patients with recurrent malignant gliomas as measured by patients who obtain either a radiographic response or achieve 6-months of disease stabilization (6 month progression free survival). Patients will receive the dose of both agents determined from the phase I study. There is no intra-patient dose escalation.

An important limitation of prior studies of targeted molecular agents in GBMs is the lack of tumor tissue to determine whether the therapeutic agents under evaluation inhibited their putative molecular targets. We previously demonstrated such analyses are possible through a surgical substudy in which patients who undergo cytoreductive surgery for recurrent disease receive study drug pre-operatively and then restart the agents upon recovery from surgery.([name] *et al.* 2005) Therefore, in this study up to 10 patients enrolling into the phase II component will undergo resection of their tumor as part of the trial. These patients will receive temsirolimus and perifosine pre-operatively at the dose determined by the phase I. Tumor specimens resected in this manner will be analyzed for evidence of inhibition of PI3K/AKT/mTOR/S6K and RAS/MEK/ERK signaling by immunohistochemistry of

Amended:

Reviewed by OCR, JR 3/24/14

Memorial Sloan Kettering Cancer Center
IRB Protocol

IRB#: 09-058 A(14)

paraffin embedded tissue and Western blot of flash frozen tissue. PTEN, p-AKT, p-mTOR, total S6K, p-S6K, p-ERK, Ki-67, and apoptosis will be measured. These data will be compared to similar analysis performed on tumor tissue not exposed to temsirolimus and perifosine obtained from each patient's original or prior surgery (intra-patient comparison). After recovery from surgery, patients will resume treatment with temsirolimus and perifosine. Treatment duration will be measured in 4 week cycles.

Phase I and II

Patients will remain on treatment as long as there are no unacceptable toxicities until tumor progression. Responses will be assessed by MRI scans every 8 weeks. Fluorodeoxyglucose (FDG)-PET will be performed in phase II patients to evaluate the effects of the drugs on tumor metabolism. Paraffin tumor sections from the original surgical resection will be obtained from all patients. An attempt will be made to correlate the genotype patient's tumor specimens with response to treatment. In this way, molecular subsets of malignant gliomas that may be more or less likely to respond to treatment with temsirolimus and perifosine can be identified.

2.5 Correlative Studies Background

GBMs are molecularly heterogeneous. For example, the oncogenic mutations driving tumor growth differ between "primary" (or "de novo") GBMs which appear abruptly and "secondary" GBMs which arise from lower grade gliomas.(Kleihues and Ohgaki 1999) Similarly, tumors with *MGMT* promoter methylation appear to exhibit greater sensitivity to temozolomide and are associated with longer overall survival regardless of therapy in comparison to tumors with unmethylated promoters.(Hegi *et al.*, 2005) Finally, recent results also suggest a tripartite distribution of high grade gliomas (with prognostic significance) designated proneural, proliferative, and mesenchymal. (Phillips *et al.*, 2006)

This molecular heterogeneity is of potential importance in clinical trials. An experimental chemotherapy regimen may be declared ineffective during a trial involving GBMs of all molecular profiles despite responses in a small subset. For example, the EGFR inhibitors erlotinib and gefinitib as monotherapy are ineffective in recurrent GBMs when all tumors are analyzed as one cohort, associated with 6mPFS rates and response rates that are no better than historic controls (Lieberman *et al.*, 2003; Raizer *et al.*, 2004; Rich *et al.*, 2004; Vogelbaum *et al.*, 2004; Yung *et al.*, 2004) However, analysis of archival tissue in one study demonstrated that a specific molecular profile, present in only 10-15% of patients, strongly correlated with activity in the small subset of patients exhibiting radiographic responses.(Mellinghoff *et al.*, 2005) Although others have questioned this conclusion, (Brandes *et al.*, 2008), the concept that treatment may be active in tumors with a specific molecular profile is important. Molecular profiling may allow identification of a subset of tumors sensitive to a particular therapy that would otherwise be declared inactive. Such identification may then allow individualization of therapy. In this trial, we also propose to molecularly profile archival tissue with the goal of determining the subset of patients more likely to respond.

In addition, a subset of patients on the phase II study will receive dual drug therapy followed by surgical resection of tumor. This provides an opportunity to assess the molecular effects of therapy in humans *in vivo*. We will perform the above analysis for PI3K/AKT/mTOR/S6K and RAS/MEK/ERK signaling, proliferation, and apoptosis, using intrapatient comparison from pre-treatment archival tissue from an earlier resection as we have done in other studies. ([name] *et al.*, 2005)

Amended:

Reviewed by OCR, JR 3/24/14

3 PATIENT SELECTION

3.1 General Eligibility Criteria

- 3.1.1 Patients must have unstained slides or tissue blocks available from at least one prior surgery. Frozen tissue is also requested if available.
- 3.1.2 Patients must have received prior radiotherapy and temozolomide. There is otherwise no limit on the number of prior recurrences/therapies.
- 3.1.3 At least 6 weeks (42 days) must have elapsed since completion of radiation therapy to initiation of study treatment.
- 3.1.4 At least 4 weeks (28 days) must have elapsed since most recent temozolomide and initiation of study treatment.
- 3.1.5 Patients must have recovered from the toxic effects of other prior direct inhibitors of VEGF/VEGFR: 4 weeks from prior therapy with agents such as bevacizumab (Avastin), afibbercept (VEGF-Trap), cediranib (AZD2171), or XL-184 (BMS 907351); any questions regarding the definition of a direct anti-VEGF/VEGFR therapy must be discussed with the PI or co-PI. Patients must have recovered from the toxic effects of other prior therapy including: 4 weeks (28 days) from any investigational agent, two weeks (14 days) from vincristine, 6 weeks (42 days) from nitrosoureas, 3 weeks (21 days) from procarbazine administration, and 1 week (7 days) for non-cytotoxic agents, e.g., interferon, tamoxifen, thalidomide, cis-retinoic acid, etc. (radiosensitizer does not count), and 4 weeks (28 days) from any other prior cytotoxic therapy. Any questions related to the definition of non-cytotoxic agents should be directed to the co-PI.
- 3.1.6 Patients must have shown unequivocal evidence for tumor progression by MRI/CT on the baseline MRI/CT in comparison to a prior scan OR have recently undergone resection for recurrent/progressive disease per 3.1.17. The baseline brain MRI/CT must be performed 14 days or fewer prior to treatment. The same type of scan, i.e., MRI (or CT for patients who cannot undergo MRI) must be used throughout the period of protocol treatment for tumor measurement. Criteria in [section 11](#) for progression on this study are not mandatory if the disease progression is obvious in the opinion of the investigator. Any questions should be addressed to the PI.
- 3.1.7 Patients must be on a stable or decreasing dose of corticosteroids for a minimum of 5 days before the baseline MRI/CT (and PET scans for patients on the phase II study) *except* patients undergoing surgery on the surgical substudy of phase II ([section 5.1.1.7](#)). If the corticosteroid dose is increased between the date of imaging and registration a new baseline MR/CT is required.
- 3.1.8 Age ≥ 18 years. Because no dosing or adverse event data are currently available on the use of temsirolimus in combination with perifosine in patients <18 years of age, children are excluded from this study, but will be eligible for future pediatric phase 1 combination trials.
- 3.1.9 Karnofsky Performance Status $\geq 60\%$
- 3.1.10 Life expectancy of greater than 8 weeks.
- 3.1.11 Patients must have normal organ and marrow function (WBC $\geq 2,000/\mu\text{l}$, ANC $\geq 1,500/\text{mm}^3$, platelet count of $\geq 100,000/\text{mm}^3$, and hemoglobin $\geq 10 \text{ gm/dl}$), adequate liver

Amended:

Reviewed by OCR, JR 3/24/14

Memorial Sloan Kettering Cancer Center
IRB Protocol

IRB#: 09-058 A(14)

function (SGOT, SGPT and bilirubin < 2 times ULN), adequate renal function (creatinine < 1.5 mg/dL), calcium levels at or above the lower limit of normal, and phosphorus levels at or above the lower limit of normal before starting therapy. These tests must be performed within 14 days prior to registration. Eligibility level for hemoglobin may be reached by transfusion.

3.1.11.1 Platelet count of at least 100,000/mm³ on at least 2 consecutive blood draws, at least 1 week apart, with results stable/trending upward. Any question regarding the definition of stable/trending upward must be discussed with the PI.

3.1.12 Patients must have cholesterol level \leq 350 mg/dl and triglycerides level \leq 400 mg/dl because temsirolimus can induce hyperlipidemia.

3.1.13 Women of child-bearing potential and men must agree to use adequate contraception (hormonal or barrier method of birth control; abstinence) prior to study entry and for the duration of study participation because the effects of temsirolimus and perifosine on the developing human fetus are unknown. Should a woman become pregnant or suspect she is pregnant while participating in this study, she should inform her treating physician immediately.

3.1.14 Women of childbearing potential must have a negative B-HCG pregnancy test documented within 7 days prior to treatment.

3.1.15 Women must agree not to breast feed.

3.1.16 Patients must have the ability to understand and the willingness to sign a written informed consent document.

3.1.17 As a primary efficacy endpoint is 6mPFS rate, measurable disease is not required for eligibility in patients who recently underwent resection as long as progressive disease led to the surgery, and the histology of the most recent surgery documented recurrent/progressive/persistent malignant glioma.

3.1.17.1 If cytoreductive surgery is planned for tumor recurrence at the time of enrollment, such patients may be eligible for the surgical substudy (Phase II only), taking temsirolimus + perifosine pre-operatively and then re-initiating such therapy after recovering from the effects of surgery ([section 5](#)).

Phase I specific inclusion criteria:

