In a subchronic toxicity study in rats, dose dependent toxicities were observed in the kidneys, gastrointestinal tract, skin, mammary glands, pituitary, hematopoietic tissue, spleen, ovaries, male genital tract, and eyes (Perifosine Investigator's Brochure, 1998). Effects on the hematopoietic tissue were characterized by an increase in cellularity for the bone marrow and an increased extramedullary hematopoiesis. Histopathologic changes seen in other tissues included evidence of chronic nephropathy, atrophy of hair follicles, atrophy of mammary glands, reduction of follicular development in the ovaries, degeneration of the germinative epithelium of the testes, atrophy/inactivation of prostate and seminal vesicals, secondary hypertrophy of the Leydig cells in the testes, and hypertrophy/hyperplasia of mucosal epithelium cells in stomach and small intestine. All toxicities, except those in the male genital tract and eyes, were reversible within 13 weeks. Most significant and not clearly reversible were ophthalmologic lesions, specifically, retinal degeneration and cataract formation. This toxicity was seen in rat but not in dog toxicity studies. Clinical chemistry revealed reversible increases in CK, BUN, SGOT, SGPT and reversible decrease of red blood cell parameters, total cholesterol, triglycerides, inorganic phosphorus and albumin and total protein.

In dogs, decreased food consumption, anorexia, diarrhea and vomiting were noted. Clinical chemistry

Amended:

Reviewed by OCR, JR 3/24/14

Memorial Sloan Kettering Cancer Center
IRB Protocol

IRB#: 09-058 A(14)

revealed reduced glucose levels in the group receiving the highest dose. All changes were reversible during a 6-week recovery period. Histopathologically, minimal to mild degeneration of proximal tubular cells of the kidneys were found in male animals.

Reproductive Toxicity

Perifosine impaired fertility and reproductive performance in male rats at doses of 2.37 and 8.25 mg/kg. Perifosine impaired the reproductive performance of female rats and possessed fetotoxic properties in doses of 3.16 and 21.5 mg/kg. A dose of 0.464 mg/kg is considered to be the no-observed-toxic-effect level on the female reproductive function and early embryonic development.

Mutagenicity/Carcinogenicity

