In the assay systems employed (Salmonella typhimurium reverse mutation assay with and without S9-Mix, the V79 gene mutation test, and the micronucleus test *in vivo*) only a slightly increased number of mutants was found in the V79 gene mutation test without activation, a finding similar to that for miltefosine. Carcinogenicity studies of perifosine are not available; thus, a carcinogenic potential of perifosine cannot be excluded.

Clinical Results - Phase 1

Asta Medica sponsored three European phase 1 trials of perifosine evaluating weekly and daily dosing, as well as an enteric coated formulation. The study D-21266-3040 was a phase 1 study of escalating doses of perifosine given on a weekly schedule. Thirty-six patients were treated in sequential cohorts at dose levels of 100, 200, 350, 450, 600 and 800 mg/week. At 350 mg weekly, vomiting grade 3 occurred in the first two patients. These patients responded to anti-emetic prophylaxis with tropisetron, alizaprid, and dexamethasone, and all subsequent patients received anti-emetic prophylaxis. Among 7 patients treated at the maximum administered dose of 800 mg/wk, grade 2 nausea and vomiting of residual perifosine tablets and grade 4 diarrhea occurred. Preliminary data from analyzed plasma samples of patients receiving perifosine in the dose range of 100 to 600 mg indicated a dose-linearity of C_{max} and of the area under the concentration time curve (AUC) in this dose range. However, at 800 mg/week, the dose-AUC and C_{max} proportionality was reduced. C_{max} and $t_{1/2}$ values ranged from 8 – 25 hours and 96 – 225 hours, respectively (Perifosine Investigator's Brochure, 1998). After repeated dosing a slight accumulation of perifosine was seen, which is in accordance with the relatively prolonged terminal $t_{1/2}$ of the agent. Perifosine was not detectable in the patients' urine. One patient with chondrosarcoma treated at 350 mg/weekly achieved a partial response (Asta Medica update to the NCI, 2000).

In the phase 1 study D-21266-3079, 22 patients received perifosine at escalating doses of 50-350 mg daily x 21 days. Fatigue, nausea, vomiting and diarrhea were the most frequent toxicities experienced by patients on this study. The maximum tolerated dose on this study was 200 mg/day. Three of six patients treated at 250 mg/day and the one patient treated at 350 mg/day had intolerable fatigue and/or gastro-intestinal toxicity. (Asta Medica update to the NCI, 2000)

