An enteric-coated formulation was evaluated on a weekly study in the trial D-21266-3087. A total of eight patients (4/dose level) were treated at 200 or 350 mg weekly. The enteric coating did not improve the tolerability of the oral administration of perifosine and reduced its bioavailability. (Asta Medica update to the NCI, 2000)

The Division of Cancer Treatment and Diagnosis, National Cancer Institute has sponsored two phase 1 trials of perifosine evaluating a loading dose followed by daily maintenance dose schedule. A loading dose/daily maintenance schedule was proposed due to improved efficacy in the DMBA-induced rat mammary carcinoma model with this schedule and the clinical PK data which showed a long terminal

Amended:

Reviewed by OCR, JR 3/24/14

Memorial Sloan Kettering Cancer Center
IRB Protocol

IRB#: 09-058 A(14)

$t_{1/2}$ of ~ 100 hours and a slow approach to steady state. A loading dose could potentially achieve active anti-tumor serum concentrations followed by tolerable daily maintenance dosing. The loading dose was fractionated and administered every 6 hours to avoid potential problems with bioavailability and possible C_{max} associated toxicity such as emesis. Similar to the results from the Asta Medica-sponsored studies, the most frequently observed toxicities in NCI sponsored phase 1 studies were gastrointestinal (nausea, vomiting, diarrhea) and fatigue. Chronic nausea among patients receiving perifosine appears to resolve approximately 48 hours following discontinuation of therapy. In contrast, fatigue may persist for weeks after therapy has ended.

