3.2 Exclusion Criteria

3.2.1 Patients may not be receiving any other investigational agents.

3.2.2 Patients must not have a history of allergic reactions attributed to compounds of similar chemical

Amended:

Reviewed by OCR, JR 3/24/14

or biologic composition to temsirolimus or perifosine.

3.2.3 Patients must not be taking EIAED. If previously on an EIAED, the patient must be off of it for at least two weeks prior to treatment on study.

3.2.4 Patients must not have uncontrolled intercurrent illness including, but not limited to, ongoing or active infection, symptomatic congestive heart failure, unstable angina pectoris, cardiac arrhythmia, or psychiatric illness/social situations that would limit compliance with study requirements.

3.2.5 Pregnant women are excluded from this study because temsirolimus and perifosine are agents with the potential for teratogenic or abortifacient effects. Because there is an unknown but potential risk for adverse events in nursing infants secondary to treatment of the mother with temsirolimus or perifosine, breastfeeding should be discontinued if the mother is treated with temsirolimus and perifosine.

3.2.6 HIV-positive patients on combination antiretroviral therapy are ineligible because of the potential for pharmacokinetic interactions with temsirolimus and perifosine. In addition, these patients are at increased risk of lethal infections when treated with marrow-suppressive therapy. Appropriate studies will be undertaken in patients receiving combination antiretroviral therapy when indicated.

Phase II specific exclusion criteria

3.2.7 Patients may not have received prior treatment with mTOR inhibitors such as temsirolimus, rapamycin (sirolimus), or RAD001 (everolimus). Any question regarding the definition of mTOR inhibiting therapy must be discussed with the PI. Such prior therapy is allowed for the phase I component.

3.2.8 Patients may not have previously received perifosine or other AKT targeting agents. Any question regarding the definition of AKT targeting therapy must be discussed with the PI. Such prior therapy is allowed for the phase I component.

3.2.9 Patients must not have received prior treatment with convection enhanced delivery, other catheter based intra-tumoral treatment, or carmustine (BCNU)/Gliadel wafers because of potential difficulty interpreting brain scans in such patients. Such prior therapy is allowed for the phase I component.

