5.5 Duration of Follow Up

Patients will be followed every 3 months for survival after removal from study. Patients removed from study for unacceptable adverse events will be followed until resolution or stabilization of the adverse event. They should then be followed for survival every 3 months.

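### Contraception and pregnancy notification (3.1.13) end with study participation, possibly a day after the last perifosine dose, although the drug's half-life is about 100 h (range 96–225 h) and it is fetotoxic in rats

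*Combined protocol and SAP*

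**What the plan says.** Section 3.1.13 asks women of child-bearing potential and men to use contraception "prior to study entry and for the duration of study participation", on the ground that the effects of both drugs on the human fetus are unknown. The duty to tell the physician begins "Should a woman become pregnant or suspect she is pregnant while participating in this study", so it has the same end point. Participation is not defined.

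Under 5.4 and 5.6 a patient is removed from the study when a listed criterion applies, and disease progression is first on the list. Section 5.5 puts later contact outside the study: "Patients will be followed every 3 months for survival after removal from study". Perifosine maintenance is taken nightly (5.1.1.5).

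On hazard, section 2.1 states: "Perifosine impaired the reproductive performance of female rats and possessed fetotoxic properties in doses of 3.16 and 21.5 mg/kg". It adds: "A dose of 0.464 mg/kg is considered to be the no-observed-toxic-effect level on the female reproductive function and early embryonic development". It also reports impaired fertility in male rats at 2.37 and 8.25 mg/kg, and toxicity of the male genital tract that was not among the effects reversing within 13 weeks. Section 3.2.5 excludes pregnant women because "temsirolimus and perifosine are agents with the potential for teratogenic or abortifacient effects".

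On persistence, section 2.1 gives ranges for the weekly phase 1 study, the second being the half-life: "ranged from 8 – 25 hours and 96 – 225 hours, respectively". For the loading-dose rationale it uses a terminal half-life "of ~ 100 hours and a slow approach to steady state". The temsirolimus half-life is about 15 h.

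**The concern.** The reason given for contraception applies for as long as drug remains in the body, but the rule stops at an administrative event. Followed as written, a woman removed for progression may stop contraception the next day, while most of the perifosine from her last doses is still present. If she then conceives, the pregnancy falls outside the notification sentence. Pregnancy tests precede each 4-week cycle (5.1.3.2, 5.1.3.3), so none is scheduled after the last one. The requirement binds men as well, and the male rat findings make an early end no easier to defend for them.

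The protocol does look beyond the last dose elsewhere. Adverse events are reportable for 30 days after it, and some for longer (7.4, 7.4.1). Anticoagulated patients are monitored for at least 2 weeks after stopping (5.3.9). Contraception has no such period.

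**Working it through.** The protocol has no derived figure to reproduce here. The check takes its reported half-lives and asks how much drug remains when the duties can lapse.

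**Inputs.** Perifosine half-life: about 100 h, range 96–225 h (2.1). Temsirolimus half-life: about 15 h (2.1). Shortest interval from last perifosine dose to removal: about 24 h, inferred from nightly dosing and from removal when a 5.4 criterion applies.

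**Assumptions.** First-order elimination, so the fraction remaining is 2^(−t / half-life). Washout is taken as five half-lives, which leaves 2^(−5) = 3.1%; the protocol sets no washout convention.

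**Perifosine after the last dose.**

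| Time since last dose | Half-life 100 h | Half-life 225 h |
|---|---|---|
| 1 day (24 h) | 85% | 93% |
| 7 days (168 h) | 31% | 60% |
| 14 days (336 h) | 10% | 36% |
| 21 days (504 h) | 3% | 21% |
| 30 days (720 h) | 0.7% | 10.9% |

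**Time to five half-lives.**
- 96 h: 5 × 96 / 24 = 20.0 days
- 100 h: 5 × 100 / 24 = 20.8 days
- 225 h: 5 × 225 / 24 = 46.9 days
- Temsirolimus: 5 × 15 / 24 = 3.1 days

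Perifosine therefore sets the period. No half-life is given for sirolimus, the main temsirolimus metabolite.

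**Patients with a shorter gap.** Those taken off study for unresolved toxicity have already been off both drugs for more than 14 days (6.1.3.1, 6.1.4). At most 20.8 − 14 = 6.8 days remain for them at 100 h, and 46.9 − 14 = 32.9 days at 225 h.

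**Candidate period of 8 weeks.** 56 × 24 = 1344 h; 1344 / 225 = 5.97 half-lives; 2^(−5.97) = 1.6% remaining at the slowest reported elimination. A 30-day period would leave 10.9% there.

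**The case against.** The strongest objection is that participation is undefined. Patients stay under protocol-directed follow-up after treatment, and if that counts as participation the gap disappears. But 5.5 places survival follow-up after removal from study, and the wider reading would require contraception until death. The ambiguity is real; a date counted from the last dose settles it on either reading.

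The consent pages were not available and may state a longer period. That stands, and it limits the point to the protocol text.

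The practical risk may be small. The accrual table in 13.2 has 16 women among 42 patients (maximum enrolment is 92), the number of reproductive potential is not given, and section 2.3 puts median survival in recurrent GBM at 6 months. Human fetal harm at residual levels is not shown: there is a rat no-effect level of 0.464 mg/kg and no scaling to human exposure. This tempers the severity, but the missing scaling also means the protocol offers no basis for assuming safety.

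Section 7.4.1 requires birth defects after treatment to be reported. That is a partial safeguard acting on outcome only: it neither prevents exposure nor captures every pregnancy.

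Finally, 8 weeks rests on an assumed convention applied to the top of a range from preliminary weekly-dosing data; at 100 h the same rule gives about 21 days. It is also set by drug persistence and not by the male reproductive findings. Both remarks are fair, and they are reasons to treat 8 weeks as a minimum that the clinical team may lengthen.

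**Conclusion.** The concern holds. The visible protocol does not extend contraception or pregnancy notification past the end of participation, which can come about a day after the last perifosine dose. Both duties can then lapse about 20 to 47 days before five half-lives have passed, or at most about 7 days (100 h) to 33 days (225 h) before for patients already off drug for 14 days. This rests on first-order elimination, the five-half-life convention, and reading participation as ending at removal. It is a patient-safety point that should be corrected, held with medium confidence because the term is undefined, the consent form was not seen, and harm at residual human levels is unproven.

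**What to change.** In 3.1.13, replace the end point of the contraception requirement with: *during treatment and for at least 8 weeks after the last dose of study drug*. Extend the pregnancy-notification sentence to the same date, and repeat that date in 5.5. The clinical team may set a longer period, and should consider the male rat findings when deciding whether 8 weeks is enough for men. Check the consent form and align it if it repeats the present wording.

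The cost is a minor protocol amendment with IRB review, and a consent revision if needed. No visit, test or patient is added. The downside is a longer contraception commitment for participants.
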